10.3.8 Take Home Questionnaires

Provide the participant with a packet of the following questionnaires to take home and complete at her leisure. She may also choose to fill them out at the clinic or to start filling them out at the clinic and then take them home. All of these options are acceptable.

Instruct the participant to fill out questionnaires using the same techniques that staff use for Teleforms:

- use a black pen
- make corrections by drawing a line or an X through the wrong bubble, and filling in the correct one
- read the instructions at the top of each page and/or before each question
- fill in the bubbles completely
- participants should not mark anything in the banner of the forms nor make notes or comments on the forms

Ask the participant to bring back the completed questionnaires to the next visit. Provide her with a telephone number and encourage her to call if she doesn't understand the questions or is unsure about how to complete a questionnaire. **If the participant refuses or, in the judgment of the investigator, is incapable of filling out these questionnaires in a reasonably competent manner, she is not eligible to participate in PRIDE.** If this is the case, fill out the Inclusion/Exclusion Checklist by marking the "No" bubble for Inclusion Criteria Item F.

10.3.8.1 Paffenbarger Activity Questionnaire (2 pages)

Most of this questionnaire refers to the previous week's activity level. Question 1 determines if the previous week was an unusual week for the participant. If the answer to this is "Yes", the participant is instructed to choose a different week that was more "usual" when thinking about the response to each question.

Note that question 2 refers to *flights* of steps *per day* as opposed to individual steps and question 3 refers to city blocks walked *per day*. Remind the participant that the activities in question 4 should not include walking since that is recorded in question 3.

Staff may help participants complete this questionnaire as some of the

questions can be confusing.

10.3.8.2 Incontinence Impact Questionnaire (3 pages)

This is the IIQ, not to be confused with the one page 2IQ which has already been completed. The questions on the IIQ assess how much and in what ways urinary incontinence has affected the participant's quality of life. Only one response should be selected for each item.

10.3.8.3 Urogenital Distress Inventory (2 pages)

This questionnaire focuses on specific symptoms the participant may experience. Note that either the "No" or the "Yes" response should be selected for each item. If "Yes" is marked, then one of the next four bubbles should be marked.

10.3.8.4 Health & Activity Form (SF-36) (5 pages)

This is a standardized, quality of life questionnaire. Only one response should be selected for each question.

In general, these questionnaires are self-explanatory with instructions at the beginning of each page or each question. Please contact the Coordinating Center immediately if you notice that a question is constantly misinterpreted. The FFQ is more complicated and is described in more detail below.

10.3.8.5 Food Frequency Questionnaire

The PRIDE Food Frequency Questionnaire facilitates analysis of specific nutrients as well as overall dietary patterns. It is designed to be sensitive to dietary changes that are likely with the planned intervention. In addition, the opportunity to analyze and contrast dietary intake across and within intervention and control groups is likely to increase our understanding of how differences in food and beverage intake affect women with urinary incontinence, with or without weight loss.

The PRIDE FFQ is a modified Block Dietary Data Systems questionnaire. It is self-administered with limited staff support. Project

staff will provide basic instructions for completing the form and will review the form upon its return.

Here are a few reminders to help with data quality:

No other marks on the questionnaire Comments or notes should not be written on the questionnaire as they may interfere with scanning. Comments can be made on a separate page.

Bubble completely Fill in the answer bubbles completely. Do not simply make a checkmark or an 'X' over the bubble.

One bubble per answer Choose only one response in each section.

No staples Avoid using staples on the form since they must be removed prior to faxing. Marks left by staples can interfere with Teleform's tracking, form number or page number codes.

No extra pages Do not add any extra pages or papers with notes on them when faxing the form. Do not attach yellow stickies. Teleform reads only pre-defined boxes.

No folds Do not fold the questionnaire as this can interfere with faxing and interpretation.

No 3-hole punch Holes might interfere with the reading process.

A clear, positive introduction and explanation of the questionnaire is extremely important to obtain valid information and to help the participant complete the form with minimal frustration.

Although portion size improves the accuracy of the nutrient estimates, the reviewer should be aware that frequency of consumption is more important than exact portion size in determining long-term usual intake. Show the participant the first few pages of the questionnaire and point

out the headings that appear on each page referring to frequency and portion size. Be sure to give the participant the photograph page (500 copies will be provided to each site) that illustrates approximate portion sizes.

To help orient participants to the form, tell them that the items are grouped by type of food (e.g., fruits, vegetables, meats). Encourage her to glance through all the different itemized food in each category before she starts to fill out the form. Remind participants to think of foods eaten both at home and away from home. Remind them to include both meals and snacks. If participants do not prepare the food themselves, ask that they answer to the best of their ability. If the participant uses an item with a frequency that does not fit exactly into one of the available ranges, ask her to choose the closest category.

The **time frame** that the FFQ covers is "the past 6 months or so". This is deliberately a little vague because no one is expected to remember exactly what was eaten during the past 6 months. The idea is to get a usual pattern of frequency. Some respondents may comment, "Oh, I can't even remember what I ate yesterday!" It's important to make clear to participants that the idea is not to be precise, but to think about their usual pattern. For example, they don't have to remember how many times they had eggs in the past 6 months. Instead, what they can recall with reasonable accuracy is, "I have eggs about twice a week."

The participant may indicate that she has changed her habits in the past 6 months. If the change is recent ask her to report her former pattern of eating. If the change has been well incorporated and appears to be lasting and stable, she should report on the new pattern rather than the former pattern.

Emphasize completeness and that no line should remain blank. The participant should check "Never" rather than simply skip foods she rarely or never eats. Inform participants that if they don't eat a particular food, they may leave the serving size blank.

The food list represents the most important nutrient sources in most people's diets. It does not and is not intended to include all possible foods that people ever eat. Thus, it is likely that some foods that a person eats will not be on the list. Do not attempt to force unmentioned

foods into categories by guessing at their similarity.

Here are some clarifications:

Fruits

In this section, the number of times per month or week refers to number of days per month or week. For example, the respondent eats bananas on about two days a week. Then, the portion size section provides the location where the respondent can record how many pieces of that fruit she eats, on the days she eats them.

Seasonality: Among the fruits, all but one of the items refer to food intake year round. If any of these "year-round" foods are eaten more in one season than another, ask respondent for her best estimate of a year-round average.

Jams and jellies should not be counted as servings of fruit. Fruit in yogurt does not count as servings of fruit.

Bananas

All kinds, all sizes. The frequency section means "how often", not how many bananas per week. Show the participant that she should record how often first; then in "portion size" she documents "how many" on each occasion.

Fresh apples or pears

All kinds, all sizes; includes Asian pears. Discourage respondents from trying to do math, adding up separately their apples and their pears. An average is fine.

Oranges, tangerines, not including juice

All kinds, all sizes; includes tangerines, tangelos, mandarin oranges. (Orange juice is a later item.) If respondent only uses oranges to make juice, tell her to wait and count that as orange juice. And then use the glasses for portion size. If she sometimes eats them as oranges and sometimes as juice, ask her to estimate the frequency of 'as

	oranges' in the fruit section, and then later the frequency of 'as juice' in the juice section.
Grapefruit, not including juice	All kinds, all sizes.
Cantaloupe	The focus here is on cantaloupe. Other melons should be counted only if they are deep orange like cantaloupe. Do not include honeydew or other non-orange melons.
Raw peaches, apricots, nectarines, in season Applesauce, fruit cocktail, canned pears	Any type. Report frequency only for the few months when they are "in season". Frequency is average year-round frequency of consumption. Do not include canned peaches, apricots, plums, etc.
Canned, frozen or stewed peaches or apricots	Any type. Frequency is average year-round frequency of consumption.
Any other fruit...	Any fruit, canned or fresh. Year-round frequency.
Breakfast items, dairy	
Eggs, including biscuit sandwiches and Egg McMuffins	Includes real eggs when eaten as eggs, including scrambled, boiled, fried, or on sandwiches, deviled, egg salad or quiche. Do not count eggs used in cooking, such as in cakes, custards, etc. Do not count Egg Beaters, egg substitutes, or only egg whites.
Bacon	Bacon when eaten at any time, including in sandwiches.
Breakfast sausage, including sausage biscuits	This includes breakfast-type items, but not cold-cuts for sandwiches, not main-meal items like Italian or Polish sausage, and not hot-dog type sausages like German hot dogs.

	Turkey sausage should be included here.
Pancakes, waffles, French toast	With or without butter or syrup.
Cooked cereals like oatmeal, cream of wheat or grits	This refers to all cooked cereals, including cream of rice, and less common types like kasha.
Any kind of cold cereal	This is a general question about all kinds of cold cereals. The next three questions ask about specific types of cereals, however, it is not necessary to make the sum of the three types of specific cereals add up to this first general question.
Fiber or bran cereals	This includes the very-high-fiber cereals like All-Bran and the moderately high-fiber cereals like "Fruit-n-Fiber". Any cereal with the words "bran" or "fiber" in their titles may be included here. Note that the cereals should be counted even if they are eaten as a snack rather than a breakfast cereal, and regardless of whether they are eaten with milk.
Product 19, Just Right or Total	This item includes only these three cereals. These cereals contain 100% of the RDA (Recommended Dietary Allowance) for several nutrients.
Other cold cereals	This item refers to all other cold cereals, like corn flakes, rice krispies, Special K, or sweetened cereals like Frosted Flakes, etc.
Milk on cereal	This is relevant only if cereal is eaten. Otherwise, the answer is "Never".
Cottage cheese	Includes all varieties, regular or low-fat, farmer cheese or ricotta.

Other cheeses	Includes all types, regular or low-fat, hard cheese or soft cheese, natural or processed, including cream cheese. This category should not include cheese eaten in lasagna, pizza, etc.
When you eat cheese, ...	"Cheese" here refers specifically to cheese by itself, not as part of pizza, lasagna, etc.
Yogurt, frozen yogurt	Includes all varieties, with or without fruit, regular or low-fat, sweetened or artificially sweetened. Do not count the fruit in yogurt separately as fruit.
French fries and fried potatoes	Includes home cooked or restaurant fries, and "home fries".
White potatoes not fried...	Includes all forms of potatoes except fried. Do not include potatoes eaten in soups or stews, as those are captured elsewhere.
Sweet potatoes, yams	All types.
Rice, or dishes ...	This includes fried rice, Rice-a-roni, beans-n-rice, rice pudding, etc.
Stuffing or dressing	Bread or rice stuffing, or stovetop stuffing
Baked beans, chili with beans....	This includes all dried-type beans such as navy beans, red beans, etc. Bean, lentil or split pea soups may be counted here.
Corn	Fresh, frozen or canned. One ear of corn equals approximately a "B" or medium serving.
Green beans or green peas	Green beans include canned, frozen, fresh, or in salad bars. Green peas refers to canned, frozen, fresh, or in salad bars, but not to dried-type peas like black-eye peas, split

	peas.
Broccoli, cauliflower	Includes cooked or raw. Includes items from salads only if the amount comes to at least the size of a half-cup, and then only the frequency with which this vegetable itself is eaten, not the frequency that salad may be eaten.
Carrots, or mixed vegetables containing carrots...	Includes cooked or raw. Include items from salads only if the amount comes to at least the size of a half-cup.
Spinach	Includes cooked or raw. Spinach salad should be recorded here, not under salad.
Collards, mustard greens, turnip greens	This refers specifically to the dark-green, strong-flavored greens. Beet greens, for example, may be counted here. However, lighter-green leafy vegetables such as celery tops should not be counted here.
Cole slaw, cabbage etc.	Includes raw or cooked cabbage, including Chinese cabbage, and cole slaw whether homemade or from a restaurant.
Green salad	Includes all kinds of green salad that include some lettuce, whether mostly of iceberg lettuce or of other types of lettuce, and regardless of whether other vegetables are sometimes eaten in it. Spinach salad should be recorded under "spinach", and should not be double-counted here.
Raw tomatoes	Includes tomatoes eaten alone or in salad. Does not include tomato sauces, which are captured under 'spaghetti', etc. Does not include the tomatoes in tomato or vegetable soups, which are captured under that item.

Salad dressing	All types, creamy or not, including oil & vinegar.
Any other vegetable...	Includes any vegetable not already mentioned.
Vegetable soups...	Any type of vegetable soup that has a lot of carrots, or has a tomato base.
Other soups...	This is the catch-all for all other forms of soup, whether creamed or not, including "instant" soups.
Meats and main dishes	
Hamburgers, cheeseburger, meat loaf...	All sizes, at home or in a restaurant. Does not include the ground beef used in spaghetti, lasagna or pizza. Only hamburgers, etc. made with beef are to be included here. Turkey burger should not be coded here, but should be included under "chicken or turkey, roasted or broiled".
Beef including steaks, ...	Do not include beef eaten as ground beef.
Liver...	All forms.
Pork...	Do not include pork-based lunch meats.
Mixed dishes with meat...	Include any mixed dish with beef, pork, veal or lamb. Do not include beef stew reported earlier for the "carrots" item. Do not include mixed dishes with chicken.
Fried chicken...	All parts of a chicken are included (wings, thighs, breast, etc.) provided they are fried. Include McNuggets, etc.
Chicken or turkey...	Include turkey burgers here, but not chicken/turkey eaten as part of a mixed dish.

Chicken stew...	Includes any mixed dish with chicken.
Shellfish...	All forms, including clams, mussels, squid, oysters.
Tuna...	All forms of tuna except raw as sushi, light meat or dark, in oil or in water, straight or in a casserole. Portion size, however, refers to the amount of tuna, and should not include any noodles, etc., eaten with it.
Fried fish...	Home-fried, restaurant, fast food. All types of fish.
Other fish...	All other fish, after excluding fried, tuna or shellfish. Include fish eaten raw.
Hot dogs	All forms, including chicken/turkey.
Bologna...	Lunch meats, all types. Ham refers to slices for sandwiches; ham eaten as a roast or as the entree for a main meal should be reported under "pork". Do not include small amounts eaten on pizza, etc.
Spaghetti... with tomato sauce	This item should include only those pasta dishes that are eaten with tomato sauce. It can include mixed pasta items such as raviolis.
Cheese dishes without tomato sauce...	This item should not include any pasta dishes that are eaten with tomato sauce. This includes only dishes that commonly have a fair amount of cheese, such as macaroni and cheese, certain Mexican dishes that have a lot of cheese, Welsh rarebit, etc. Incidental sprinkle cheese often used on spaghetti does not make it count as a cheese dish. Cheese

sandwiches should be counted in the earlier 'cheese' item, where number of slices can be indicated.

Pizza... All forms, all sizes, all toppings.

Breads, snacks, etc.

Point out to the participant the change in the frequency categories for this section. Never and "Less than once a month" are combined and there is an additional category "2 or more times per day".

If the participant eats bread "twice per day", but has a different portion size each time, she may have difficulty coding her consumption correctly. In this case you can suggest she convert her frequency of consumption to "every day", and then code the portion size as the total number of pieces consumed each day. For example, if the participant eats two slices of bread for lunch and one slice of bread for dinner, you may code this as "Every day", and "3 slices".

Biscuits, muffins... Biscuits include homemade or from fast food places such as Kentucky Fried Chicken, McDonalds. Muffins include bran muffins, blueberry muffins, etc., but do not include English muffins, which should be included under 'Rolls,...', below.

Rolls, Hamburger buns, English muffins, ... All types, all sizes. Note that these items come as two halves. Therefore, if they only eat 1/2 a bagel, etc., the portion size should be marked as "1/2". Only a whole bagel, English muffin, hamburger bun, etc., should be marked as "1".

White bread... White, French, Italian, etc., all forms. In reporting portion size, the response is in "slices".

Whole wheat... Includes rye, pumpernickel, or other dark breads.

Cornbread...	Includes cornbread, corn muffins, corn tortillas, hush puppies.
Butter or margarine...	All forms, on bread or added to vegetables at the table. A "pat" is about one teaspoonful.
Mayonnaise...	Include all mayonnaise-type spreads.
Peanut butter	Other nut butters may also be included in this item.
Ketchup or salsa	All kinds of tomato-based condiments.
Gravy	Include meat gravies or packaged varieties.
Snacks, like potato chips...	Includes low-salt or low-fat varieties of chips. Does not include air -popped popcorn.
Peanuts, pecans...	Any nuts or seeds such as sunflower.
Crackers	Saltines, or any other crackers
Doughnuts, Danish pastry	This is intended to capture full-fat types of doughnuts and pastries. If they eat a low-fat kind of pastry such as Entenmann's coffee cake, they should report it in the next item.
Cakes, sweet rolls...	All kinds of cakes or coffee cakes, home-made or packaged, including snack cakes.
Cookies	All kinds, all sizes.
Ice cream...	All forms including ice cream bars, fast-food milkshakes, etc.
Pumpkin pie...	Include pies or puddings made with pumpkin or sweet potato. However, do not count sweet potato if it was reported as an earlier item.

Any other pies...	All forms, fruit-filled or not. Include fast-food pies.
Pudding	All kinds, including canned, ready-to-eat, and those prepared from dry mix.
Chocolate candy, candy bars	Only chocolate-covered or chocolate-based candy and candy bars should be included here. The point is the chocolate, not just any candy.

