(without shoes) to the nearest 0.5 kg. Standing height, which is measured at the screening visit only, will be measured in millimeters with a wall-mounted Harpenden stadiometer. Body mass index will be calculated from body weight and height as weight in kg divided by the square of height in meters. Body mass index will be used to verify study eligibility.

8.4.7. Waist Circumference. Waist (abdominal) circumference is an anthropometric indicator of deep adipose tissue. Measurements will be done over bare skin or underwear using a flexible, inelastic fiberglass tape measure marked in centimeters. Waist circumference will be measured at the minimum circumference, usually the umbilicus, between the iliac crests and lower ribs.

8.4.8. Food frequency questionnaire. Food intake will be assessed using a self-administered Block food frequency questionnaire to allow quantification of total energy intake and percent calories from fat. These data will be used to estimate dietary change and to provide information about adherence of participants to the weight loss program.

8.4.9. Physical activity. The Paffenbarger Activity Questionnaire⁵⁸ will be administered as a measure of physical activity. This questionnaire has been used to assess leisure time activity in many studies and can be scored to provide an estimate of calories expended per week in overall leisure time activity and in activities of light (5 kcal/min), medium (7.5 kcal/min), and high (10 kcal/min) intensity. Changes in exercise on the questionnaire have been shown to be predictive of weight change in overweight and obese individuals. Physical activity will be used to characterize adherence to the weight loss intervention and will be examined as a potential predictor of successful weight maintenance.

8.4.10. Sleep questionnaire. We will assess sleep quality using established and validated instruments, the Pittsburgh Sleep Quality Index (PSQI) and daytime sleepiness using the Epworth Sleepiness Scale (ESS) that are the standard for sleep research. The PSQI is a 19-item questionnaire that measures reported sleep patterns and sleep problems, including sleep quality, sleep latency, sleep efficiency and napping behavior.

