13.3.4 Questionnaires

Most questionnaires have been administered previously during screening or randomization visits and instructions for each can be found in Chapter 10 or Chapter 12. The Beck Depression Inventory must be completed and reviewed on-site. It might be helpful to complete the Paffenbarger on-site so that staff can assist the participant. As during screening, the Sexual Function questionnaire should be accompanied by a stamped, addressed envelope, completed off-site and sent directly to the Coordinating Center. Whether other questionnaires are completed on- or off-site is left to the discretion of study staff. All questionnaires to be completed off-site should be mailed to the participant in advance so that she can complete them at home and bring them with her to the clinic visit. Please check the list at the beginning of Section 13.2 to be sure you have administered all questionnaires.

The following questionnaires are administered for the first time at this visit.

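### The food-questionnaire rule written for screening (report the former diet if a change is recent) is reused at Months 6, 12 and 18, where it can record the wrong diet

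*Protocol*

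**What the plan says.** Operations Manual section 10.3.8.5 sets the FFQ recall frame as "the past 6 months or so" and asks for a usual pattern. If a participant says her habits changed within that frame, there are two branches. The first is: "If the change is recent ask her to report her former pattern of eating". The second covers a change that has been absorbed and looks durable; then "she should report on the new pattern rather than the former pattern". The manual does not define when a change stops being recent or starts being durable.

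The fruit section has its own time frame: "Among the fruits, all but one of the items refer to food intake year round". If such a fruit is eaten more in one season, staff are to "ask respondent for her best estimate of a year-round average". The notes for applesauce and canned pears, for canned or stewed peaches and apricots, and for other fruit ask for year-round frequency with no seasonal condition.

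On purpose, the same section says of the questionnaire: "It is designed to be sensitive to dietary changes that are likely with the planned intervention". Protocol section 8.4.8 says: "These data will be used to estimate dietary change and to provide information about adherence of participants to the weight loss program".

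There is no follow-up version of the instructions. For questionnaires already used at screening or randomization, section 13.3.4 (Month 6) says "instructions for each can be found in Chapter 10 or Chapter 12". Section 13.6.5 points back in the same way for Month 12, and section 13.7 makes Month 18 the same as Month 12.

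**The concern.** At screening a usual-diet rule is sensible, because it stops a few unusual weeks from standing in for habitual intake. At follow-up the change in diet is the quantity being measured. A rule that can replace the changed diet with the earlier one works against the purpose stated in section 10.3.8.5 and in protocol section 8.4.8.

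What is at stake is the FFQ estimate of dietary change and adherence. At Month 6 the rule could return a weight-loss participant's report to her pre-program diet. At later visits it could replace a lapse with an earlier, better diet. No form field is described that records which pattern was reported, so the analysis could not identify or correct the affected records.

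**Working it through.** The plan states no figure on this point, so there is none to reproduce. The check is one of timing.

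**Inputs**
- Visit windows after randomization: 24–28, 50–54 and 76–80 weeks (section 4.3.5).
- Delay from randomization to first group session: 0 to 30 days, that is 0 to 30/7 = 4.3 weeks (section 16.3.2).
- Portion-controlled diet: intervention weeks 3–19 (section 16.3.4).
- FFQ frame: six months, taken as 26 weeks (assumption). A literal year-round frame is 52 weeks.

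**Step 1. Age of the program at each visit**

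Age = visit week − start delay. Share of a frame after the start = min(1, age / frame length).

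| Visit | Age (weeks) | Share of 26 weeks | Share of 52 weeks |
|---|---|---|---|
| Month 6 | 24 − 4.3 = 19.7 to 28 | 19.7/26 = 76% to 100% | 19.7/52 = 38% to 28/52 = 54% |
| Month 12 | 50 − 4.3 = 45.7 to 54 | 100% | 45.7/52 = 88% to 100% |
| Month 18 | 76 − 4.3 = 71.7 to 80 | 100% | 100% |

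**Step 2. Apply the two-branch rule**

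- *Month 6.* The start of the program falls inside the six-month frame or close to its edge, so the rule on changed habits can be triggered. Which branch applies rests on two undefined terms. If the change is called recent, the pre-program diet is recorded. A second ambiguity is that the portion-controlled phase ends between 19.7 − 19 = 0.7 and 28 − 19 = 9 weeks before the visit. For a woman who stopped then, the former pattern might be the portion-controlled diet instead.
- *Months 12 and 18.* The whole frame lies after the program began. A change that is recent at these visits is a change from one on-study diet to another. If it is a lapse, the first branch has her report the better diet that came before it.

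**Step 3. Scale at Month 6 (illustration only)**

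Suppose a share p of weight-loss women report their pre-program diet, p is unrelated to the size of their true change, and the control arm is unaffected. Then

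measured mean change = (1 − p) × true mean change,

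which is 80% of the truth at p = 0.2 and 50% at p = 0.5. The documents give no value for p.

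**Step 4. Fruit items at Month 6**

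A literal 52-week look-back includes 52 − 28 = 24 to 52 − 24 = 28 weeks before randomization. This contradicts the six-month frame of the same questionnaire.

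**The case against.** The strongest reply is the second branch of the rule. At Month 6 the new diet is already about 20 to 28 weeks old, and an adherent woman could well be judged to have a settled pattern and report it. This stands. A reader might infer that dietary change in the weight-loss arm is understated throughout follow-up, but the documents do not support that. At Month 6 it is a risk that depends on staff judgment, and at Months 12 and 18 the likelier error runs the other way.

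The FFQ is also self-administered with limited staff support and may be completed at home, and the rule begins with the participant volunteering that she has changed. How often it operates is therefore unknown. For the same reason the text gives little basis for inferring that applying it would unblind assessors.

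Two further inferences should be resisted. One is that the FFQ is the only dietary measure available at follow-up. The form lists in Chapter 13 and both visit schedules contain no diet diary, but amended protocol section 8.3.5 says diet diaries are repeated at 6, 12 and 18 months; the documents disagree. The other is that the year-round wording distorts total energy or percent calories from fat, the quantities named in section 8.4.8. It applies to fruit items only, and nothing shows that they move either quantity materially.

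Finally, no numbered aim and no analysis in protocol section 12 names FFQ intake as an outcome. That limits the consequence. It does not remove the conflict between the instruction and the stated use of the data.

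**Conclusion.** The concern holds in a limited form. A screening rule that can substitute an earlier diet for the current one is carried unchanged into visits where the FFQ is meant to detect change.

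- *Month 6:* possible attenuation of the between-arm dietary difference toward zero, of unknown size. The (1 − p) figures show scale under an assumed p and are not an estimate.
- *Months 12 and 18:* possible masking of a recent lapse, which would overstate adherence.
- *Fruit items:* a year-round frame inconsistent with the six-month one, able at Month 6 to include 24 to 28 pre-randomization weeks if taken literally.

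The conclusion assumes that the six-month frame is about 26 weeks and that staff apply section 10.3.8.5 at follow-up as Chapter 13 directs. The primary voiding-diary outcome is not touched. The change is worth making because it is cheap and because the data cannot be repaired afterwards.

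**What to change.** In section 10.3.8.5, limit the former-pattern rule to screening. For Months 6, 12 and 18, instruct each woman to report her usual pattern since the previous study assessment, and never a pattern from before randomization. Adjacent visit windows lie 50 − 28 = 22 to 54 − 24 = 30 weeks apart (the same for Months 12 and 18), so this keeps a frame of about six months. Put the year-round fruit items on that same period, and refer to the follow-up wording in sections 13.3.4, 13.6.5 and 13.7.

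The cost is one paragraph in the manual and a short follow-up instruction sheet, with no added visit, form or participant. The downside is that screening and follow-up instructions differ slightly, and fruit reports at follow-up will carry some seasonal variation. Because women are randomized in waves that supply both arms (protocol section 8.2.1), that variation should be similar in the two arms.
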